6.1.2 Additional study treatments

Rosuvastatin is regarded as an Auxiliary Medicinal Product (AxMP) according to the EU Clinical Trial Regulation (EU CTR) refer to [Table 6-2](#).

Table 6-2 **Auxilliary Medicinal Products**

Treatment Title	Rosuvastatin
Treatment Description	Rosuvastatin, 5 mg, 10 mg, 20 mg, 40 mg*
Type	Drug
Dose Formulation	Tablet
Unit Dose Strength(s)	Rosuvastatin, 5 mg, 10 mg, 20 mg, 40 mg*
Dosage Level(s)	Dosage and frequency to be determined by the investigator as per local regulations
Route of Administration	Oral use
Use	Background intervention
Authorization status of the AxMP in EEA	Yes
Sourcing	Provided locally by the country or study site
Packaging and Labeling	Will be labeled as required per country requirement and local regulations.
* as commercially available	

At baseline, all participants will be switched from their individual statin to rosuvastatin with a starting dose of 5 mg/day or 10 mg/day according to the local SmPC and at the discretion of the Investigator. Participants who are already treated with rosuvastatin prior to baseline will continue treatment with their individual MTD of rosuvastatin at the discretion of the Investigator.

In addition to the treatment with inclisiran/placebo, rosuvastatin should be sequentially titrated to the MTD, if a participant's individual LDL-C is not at target (refer to [Section 3.4](#)).

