At screening, the participant's individual statin therapy will be considered along with the statin enrollment targets (refer to [Table 3-1](#)) to reflect current and prospective statin prescriptions in clinical routine.

The optional run-in period is specifically designed to continuously re-evaluate LDL-C and to titrate the participant's individual statin prescribed at screening to the individual MTD.

Participants do not need to enter the run-in period if, at screening, they are already on the MTD of a statin as documented in the participant's medical history (refer to [Section 3.1](#)).

The treatment period is a randomized placebo-controlled, double-blind period. The present study aims to demonstrate the superiority of inclisiran compared to placebo, both with an ongoing individually optimized LLT, on the efficacy of lowering LDL-C as well as on safety, tolerability and other participant-relevant endpoints.

At baseline Day 1, among other inclusion/exclusion criteria, all participants, whose MTD of statin fails to sufficiently lower LDL-C to their target set at screening, will be randomized in a 1:1 double-blind fashion to either receive inclisiran or placebo.

In addition, at baseline Day 1 all participants will be switched from their individual statin to rosuvastatin. As per current ESC/EAS guideline, treatment with a high-intensity statin therapy is recommended (Mach et al 2020). Rosuvastatin is a highly potent and well-tolerated statin. Due to its hydrophilic nature it tends to be retained in the liver rather than to diffuse out of it in non-hepatic cells, including skeletal muscle, and this hydrophilic property is suggested to account for fewer AEs (Kones 2010, McTaggart 2003).

At baseline Day 1, a participant's individual statin therapy will be switched to rosuvastatin to ensure that all participants receive the same high-intensity statin during the treatment period. Up to approximately 10% of participants who are already taking rosuvastatin at screening can be enrolled in the trial. These participants can continue receiving their MTD of rosuvastatin at baseline if in accordance with the Investigator.

Rosuvastatin should be titrated to try to achieve target LDL-C level, or to an individual MTD according to investigator discretion.

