12.5.2 Efficacy endpoints

For muscle-related AE / SMQ rhabdomyolysis / myopathy the SAF will be used for analysis. For all other secondary efficacy analyses the Full Analysis Set (FAS) will be used.

12.5.2.1 Relative change (percentage) from baseline to mean LDL-C level over the double-blind treatment period

The relative change (percentage change) from baseline in LDL-C level averaged over the double-blind treatment period will be analyzed using a mixed model for repeated measures (MMRM) including treatment group, stratification factor (cardiovascular risk category: very high risk, high risk), scheduled visit and the interaction of treatment group with scheduled visit as factors and baseline LDL-C level and the interaction of baseline LDL-C level with scheduled visit as covariates. Visit will be included as a categorical variable, and an unstructured covariance matrix will be used for the model. The null hypothesis of equal mean changes between both groups to the average over all post baseline visits will be tested by an appropriate linear contrast of the variable treatment and treatment by visit interaction. The null hypothesis will be rejected within the confirmatory testing framework, if the 1-sided p-value is <0.025 . The adjusted mean change from baseline and its corresponding 95% confidence interval will be presented.

For this endpoint a graphical presentation of the course of the regarding variable over time will be shown additionally to the analysis. Further details for this graphical presentation and for the analysis of secondary endpoints will be provided in the statistical analysis plan (SAP).

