2.3.2 Demographics and other baseline characteristics

The following participant demographic and baseline characteristics will be summarized descriptively by treatment group for the FAS:

- Age (years)
- Age groups (18 - <25 years, 25 - <45 years, 45 - <65 years, 65 - < 75 and ≥ 75),
- Age groups (18 - <65 years, 65 - < 75 and ≥ 75),
- Sex (male, female, unknown, undifferentiated),
- Country (Germany, Estonia, Latvia, Czech Rep, Spain, France, Poland, Bulgaria)
- Height (cm)
- Body weight (kg)
- BMI (kg/m^2), calculated as weight in kg divided by (height in m)²
- BMI group (< 18.5 kg/m^2 , 18.5 - <25 kg/m^2 , 25-<35 kg/m^2 , ≥ 35 kg/m^2)
- Statin use at baseline visit (% of participants on respective statin),
- Statin dose intensity at baseline visit
- CV risk category (high, very high)
- CV disease history, including but not limited to the following:
 - Myocardial Infarction
 - Unstable Angina
 - Stable Angina
 - Ischemic Stroke
 - Non-Ischemic Stroke
 - Trans ischemic Attack
 - Peripheral Artery Disease
 - Prior PCI
 - Prior stent implantation (Coronary)
 - Prior CABG
 - Primary Dyslipidaemia/ Hyperlipidaemia
 - Familial Hypercholesterolemia
 - Hypertension
 - Heart Failure
 - Atrial Fibrillation
 - Supraventricular Tachycardia

- Diabetes Mellitus
- Diabetic Retinopathy
- Diabetic Nephropathy
- Diabetic Neuropathy
- Alcohol history (Current, Never, Former)
- Smoking and vaping history (Current, Never, Former)
- Fasting Lipid profile
 - Lp(a) (nmol/L)
 - ApoB (μmol/L)
 - LDL-C (mg/dL)
 - HDL-C (mmol/L)
 - non-HDL-C (mmol/L)
 - total cholesterol (mmol/L)
 - triglycerides (mmol/L)
- relevant laboratory tests (Central lab)
 - AST (U/L)
 - ALT (U/L)
 - total bilirubin (μmol/L)
 - CK (U/L)
 - Creatinine Clearance (U/L)
 - eGFR (mL/min/1.73m²),
 - fasting glucose (mmol/L)
 - HbA1c (%)
- vital signs
 - SBP (mmHg),
 - DBP (mmHg),
 - Pulse (bpm)

Baseline values corresponding to laboratory measurements in the lipid panel refer to assessments collected on Day 1 of the study (before the first administration of the blinded investigational treatment).

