2.6.2.1 Mean relative change in LDL-C

The null hypothesis to be rejected for the relevant secondary endpoint is:

- H_{02} : The mean relative changes from baseline in LDL-C level, averaged over all post baseline visits during the double-blind treatment period, are equal between treatment groups.

The relative change (percentage change) from baseline in LDL-C level averaged over the double-blind treatment period will be analyzed using a mixed model for repeated measures (MMRM) including treatment group, CV risk category, scheduled visit and the interaction of treatment group with scheduled visit as factors and baseline LDL-C level and the interaction of baseline LDL-C level with scheduled visit as covariates. To allow adjustment for correlations between time points within participants, an unstructured variance-covariance structure will be used. The null hypothesis of equal mean changes between both groups to the average over all post baseline visits will be tested by an appropriate linear contrast of the variable treatment and treatment by visit interaction.. The adjusted mean change from baseline as well as the treatment difference and their corresponding 95% confidence intervals will be presented.

Least square means of each treatment group and estimated treatment differences at visits and corresponding 95% confidence intervals will be tabulated and presented graphically.

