5.5.3 Multiple imputation

If not stated otherwise, imputation for primary and secondary analyses will be done by the following rules: For missing data, target day of the visit is considered to assess if missing is related or not related to intercurrent event. Absolute values are imputed corresponding endpoint variables are derived on imputed data.

Select data to fit the imputation model considering strategy applied for intercurrent events:

1. For primary endpoint all observed data will be included except for data collected after intercurrent events where composite strategy is applied, e.g. data collected after PCSK-9 inhibitors will be set to missing. Note, after death no data are collected, thus no need to take any action for while alive strategy. In case of occurrence of multiple intercurrent events e.g. double-blind treatment discontinuation and later PCSK-9 use, all data RDO data up to PCSK-9 inhibitor use will be used, others will be set to missing.
2. For secondary endpoints data all observed data will be included except for data collected after intercurrent events where hypothetical strategy is applied, these will be set to missing after intercurrent event. In case of occurrence of multiple intercurrent events e.g. double-blind treatment discontinuation and later PCSK-9 use, all RDO data up to

PCSK-9 inhibitor use will be used, others will be set to missing for LDL-C analyses where hypothetical strategy is applied for PCSK-9 inhibitor use.

3. Impute missing data using MAR (missing at random):

Select all participants, impute missing values at baseline and scheduled post-baseline visits, under assumption of missing at random (MAR), using the PROC MI procedure in SAS based on the fully conditional specification (FCS statement) method for 100 times and obtain 100 imputed datasets. Missing baseline values will be imputed using a model with treatment and CV risk category. Missing Day 30 values will be imputed using a model based on values of baseline, treatment and CV risk category. The same procedure will be repeated for subsequent visits.

This results in 100 imputed datasets.

For participants in the inclisiran treatment groups who discontinued double-blind treatment prematurely, set imputed values after discontinuation of double-blind treatment to missing, if not after occurrence of other intercurrent event such as PCSK-9 inhibitor, as these will be imputed using jump to reference (J2R) in step 4.

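### The first secondary LDL-C model (H02) does not adjust for the statin under which baseline was measured, although most participants change statin on Day 1; this costs a little precision but not validity.

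*Protocol*

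**What the plan says.** **The switch.** Protocol 6.1.2: "At baseline, all participants will be switched from their individual statin to rosuvastatin with a starting dose of 5 mg/day or 10 mg/day". The next sentence makes an exception: "Participants who are already treated with rosuvastatin prior to baseline will continue treatment with their individual MTD of rosuvastatin", at the investigator's discretion. Protocol 4.1 gives the size of that group: "Up to approximately 10% of participants who are already taking rosuvastatin at screening can be enrolled in the trial".

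**Baseline.** SAP 2.1.1.5 takes the last value before the first injection. Protocol 4.1.1 requires at least 30 days on the individual MTD of a statin before that point. Baseline LDL-C is thus a value under the prior statin, which may be any drug in Table 3-2 at whatever dose is the participant's MTD.

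**The H02 model.** Besides treatment, Protocol 12.5.2.1 lists "stratification factor (cardiovascular risk category: very high risk, high risk), scheduled visit and the interaction of treatment group with scheduled visit as factors". SAP 2.6.2.1 matches it and adds "baseline LDL-C level and the interaction of baseline LDL-C level with scheduled visit as covariates", as the protocol does. SAP 5.5.2.1 writes out the same equation. None of the three has a term for prior statin.

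**Where prior statin does appear.** SAP 2.3.2 lists "Statin dose intensity at baseline visit" for the baseline table, next to statin use. Randomization is stratified by cardiovascular risk category only (Protocol 6.4.2).

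**Imputation.** SAP 5.5.3: "Missing Day 30 values will be imputed using a model based on values of baseline, treatment and CV risk category", with the procedure repeated for later visits.

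**The concern.** Take two participants in the same arm with the same baseline LDL-C. One reached it on a weak regimen from a moderate untreated level, the other on a strong regimen from a high untreated level. After both move to a similar rosuvastatin starting dose, their expected percent changes differ. A third participant who continues rosuvastatin has no switch effect at all. Baseline LDL-C cannot separate these three, because it mixes untreated level with prior therapy.

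The switch component is determined before randomization and its source is recorded. Leaving it in the residual widens the confidence interval for the LDL-C effect. At stake is the tightness of that estimate, in a trial meant to support health technology assessment. The validity of the test is not at stake.

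**Working it through.** **1. A plan figure to reproduce.** There is none. The sample size of about 880 per arm rests on the primary endpoint, with its response rates redacted. No SD, effect size or power is given for H02, and Table 3-1 gives caps on statin use, not an expected mix. The SDs, shifts and statin effects below are therefore assumptions.

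**2. Inputs from the documents.** 880 per arm, 1:1; 1776 actually randomized; one-sided alpha 0.025. H02 carries 80% weight in its family, so it faces 0.8 × 0.025 = 0.020 if H03 is not rejected (SAP 2.6.2.5). Only central-laboratory LDL-C is used (SAP 2.1.1.10), which after baseline means Days 60, 90, 150, 330 and 360.

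**3. Effect of a covariate on the standard error.** SE = SD × sqrt(2/880). A baseline covariate with partial R² (given the terms already in the model) multiplies the SE by sqrt(1 − R²).

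| Partial R² | SE reduction | Equivalent participants per arm of 880 |
|---|---|---|
| 2% | 1.0% | 18 |
| 5% | 2.5% | 44 |
| 10% | 5.1% | 88 |
| 20% | 10.6% | 176 |

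**4. How large R² might be.** Four sets of simulations, on different assumptions, give this cut in the variance of the treatment effect:

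- Prior-statin lowering of 30/40/50% in 25/45/30% of participants, post-baseline log-scale SD 0.20 to 0.40: variance ratios 0.821 to 0.961, a cut of 4% to 18%.
- Lowering spread halved (35/40/45% or 40/45/50%), same mix: 1.3% to 5.4%. With the mix also moved toward higher intensity: 0.6% to 4.4%.
- 1776 participants, baseline at or above target, the actual central-laboratory visits, 8% on prior rosuvastatin: 1% to 14%.
- Additive shifts at the switch of ±8, ±15 or ±20 points, residual SD 28, 1776 participants, 1000 replicates: SE cuts of 2.0%, 6.8% and 11.4% if the shift persists equally in both arms, and 0.8%, 3.0% and 5.1% if titration shrinks it to 30% in the placebo arm. On the variance scale the extremes are 1 − 0.992² = 1.6% and 1 − 0.886² = 21.5%.

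Roughly 1% to 18% covers all but the outer edges (0.6%, and 21.5% for the largest shift persisting undiminished).

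**5. Bias and type I error.** In the last set, estimates with and without the factor agreed to within 0.04 points in every setting (for example −20.03 and −20.01). With no true effect and a shift equal in both arms, rejection at nominal 0.020 was 0.018 to 0.024 without the factor and 0.015 to 0.027 with it; Monte Carlo error is sqrt(0.02 × 0.98/1000) = 0.004.

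**6. Does it move the H02 decision?** Power = Φ(d/SE − 2.054) at one-sided 0.020.

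| SD | SE | True difference | Power now | Power at R² 10% |
|---|---|---|---|---|
| 30 | 1.43 | 5 points | 92.5% | 94.9% |
| 30 | 1.43 | 10 points | >99.9% | >99.9% |
| 40 | 1.91 | 5 points | 71.5% | 76.1% |
| 40 | 1.91 | 10 points | 99.9% | >99.9% |

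For SD 40 and 10 points: 10/1.907 − 2.054 = 3.19, so 99.9%. The only percent-change effect in the documents is the 44% to 54% time-averaged reduction from the earlier phase III trials (Protocol 1.1). Optimized therapy in the placebo arm may shrink it here.

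**7. In terms of the interval.** At SD 30 the 95% half-width is 1.96 × 1.43 = 2.80 points. A variance cut of 1% makes it 2.79; a cut of 18% makes it 2.80 × sqrt(0.82) = 2.54.

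**The case against.** The strongest reply is that this is preference. The model already has the stratification factor, baseline LDL-C by visit and an unstructured covariance. No error is alleged and no decision would change. The size rests on assumed statin potencies and an assumed mix; requiring everyone to be at MTD may compress the spread, and titration from Day 30 may dilute the switch effect before the first central value at Day 60. The argument could also be made for other lipid-lowering drugs at baseline (up to about 20%).

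Most of this stands, and it is why the lower end is about 1%. On dilution the simulations differ: where participants above target were titrated it made little difference, whereas attenuation imposed on the placebo arm halved the gain or more. The comparison with other lipid-lowering drugs is weaker: Protocol 3.4 recommends leaving those unchanged at baseline, while the statin is changed by design. What remains is a recorded pre-randomization factor tied to the trial's own Day 1 procedure, at almost no cost.

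A reader might also infer that imputed LDL-C is materially harmed. The documents do not support that. Imputation proceeds visit by visit, so a participant with one observed value after the switch already carries its effect forward. The gap is confined to those without such a value, and no gain there has been quantified.

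**Conclusion.** The point holds as a low-severity improvement in precision. The H02 model omits a baseline factor that the Day 1 switch makes prognostic. Under assumed inputs, including it would cut the variance of the treatment effect by roughly 1% to 18%. Where in that range the trial falls cannot be settled from the documents.

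Three stronger readings should be resisted:

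- **That the H02 test is biased or its error rate inflated.** Prior statin is fixed before a 1:1 randomization, and the simulations show neither.
- **That H02 lacks power.** At assumed SDs of 20 to 40, power is at least 99.9% for true differences of 10 points or more with or without the factor. It moves noticeably only near 5 points or below.
- **That everyone is reset to 5 or 10 mg.** The sentence after the one quoted exempts prior rosuvastatin users. That exception adds to the heterogeneity and is a reason to give the group its own level.

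Nothing here judges the switching rule or any dose.

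**What to change.** Before database lock and unblinding:

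1. **Define the factor.** SAP 2.3.2 lists baseline statin dose intensity but sets no categories. Define a baseline statin group by intensity, with a separate level for participants continuing rosuvastatin. Derive it from the statin recorded before the first injection, so that it stays a pre-randomization variable.
2. **Add it to the H02 model.** In SAP 2.6.2.1 and 5.5.2.1, include baseline statin group and its interaction with visit.
3. **Use it in the LDL-C imputation.** In SAP 5.5.3, add the same factor for consistency with the analysis model, without claiming a quantified gain.

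If the sponsor prefers to keep the H02 model as it stands, a pre-specified sensitivity analysis with the factor is the minimum.

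The cost is SAP wording, the work of agreeing the categories, and a few model degrees of freedom out of about 1776 participants. No new data are needed.

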6.1.3 Treatment arms/group

Participants will be randomized at the baseline visit (Day 1) to one of the following two double-blind treatment groups in a 1:1 ratio.

- a. Inclisiran sodium 300 mg s.c.
- b. Corresponding placebo

Each participant will receive one injection of blinded inclisiran or placebo on Day 1, a second injection of blinded inclisiran or placebo on Day 90 and a subsequent injection of blinded inclisiran or placebo on Day 270, unless there is a need for discontinuing inclisiran/placebo in the course of the study (refer to [Section 3.4](#) and [Section 10.2](#)).

In addition at Day 1, each participant will be switched to open label study treatment, rosuvastatin, and receive one dose of rosuvastatin every day from Day 1 to Day 360 during the treatment period, as per individual titration, unless there is a need for discontinuing rosuvastatin in the course of the study (refer to [Section 3.4](#) and [Section 10.2](#)).

6.1.4 Treatment duration

Participants who complete participation in this trial and continue to derive clinical benefit from the study treatment based on the investigator's evaluation may receive post-trial access. Post-Trial Access (PTA) means the provision of study treatment to trial participants following their completion of trial participation. PTA will be provided until one of the following is met: participant no longer derives clinical benefit, investigator discontinues study treatment, launch or reimbursement (where applicable), **CCI** [REDACTED].

The PTA mechanism must comply with local laws and regulations in the participating trial countries. If Novartis discontinues the PTA for this trial, Novartis will work with investigators to transition participants onto locally available alternative treatment, or standard of care.

The planned study treatment duration is 360 days. In addition, a safety follow-up call will be conducted 30 days after the EOS visit.

Participants may be discontinued from the trial earlier due to safety reasons, at the discretion of the Investigator or the participant. They will continue to be followed up in the study until safety recovery or until EOS as per Assessment Schedule ([Table 8-1](#)).

6.2 Other treatment(s)

6.2.1 Concomitant therapy

LLT used by the participant in the 6 months prior to screening must be recorded on the appropriate eCRF pages.

All other medications, procedures, and significant non-drug therapies (including physical therapy and blood transfusions) used by the participant in the 3 months prior to screening must be recorded on the appropriate eCRF pages, independent of whether they will be continued during the study or not. Each concomitant drug must be individually assessed against all exclusion criteria.

Concomitant lipid-lowering therapy

In addition to the treatment with inclisiran/placebo and MTD of rosuvastatin, a participant's individual LLT has to be further escalated throughout the trial, if LDL-C is not at target. The participant's individual LLT should be complemented with ezetimibe (guideline recommendation Class I, Level B). If the LDL-C target is still not achieved, consider use of bile acid sequestrants (guideline recommendation Class IIb, Level C) ([Mach et al 2020](#)). Recently approved bempedoic acid may also be considered to be used, however, it is not depicted in the current guidelines and should thus be used secondarily after the aforementioned substances for further escalation of LLT. Concomitant PCSK9 mAb can be considered if a participant is deemed eligible by the Steering Committee. If the participant is deemed eligible for PCSK9 mAb treatment, then the blinded investigational treatment (inclisiran/placebo) will need to be discontinued. The Investigator's treatment decision as well as deviation from the above recommended LLT escalation need to be well documented on the appropriate eCRF pages. (See [Figure 3-2](#))

A new concomitant lipid-lowering drug must be assessed against all prohibited medications prior to its initiation.

Other concomitant therapy

All other medication, procedures, and significant non-drug therapies (including physical therapy and blood transfusions) administered after the participant was enrolled into the study must be recorded on the appropriate eCRF pages. A new concomitant drug must be assessed against all prohibited medications prior to its initiation.

If in doubt, the Investigator should contact the Novartis medical monitor before randomizing a participant or allowing a new medication to be started. If the participant is already enrolled, contact Novartis to determine if the participant should continue participation in the study.

